12. SAFETY AND ADVERSE EVENTS

12.1 Definitions

International Conference on Harmonisation (ICH) guidelines define an adverse event (AE) as any medical occurrence in a patient or clinical investigation subject administered a pharmaceutical product and which does not necessarily have to have a causal relationship with this treatment. An AE can therefore be any unfavorable and unintended sign (including an abnormal laboratory finding, for example) symptom, or disease temporarily associated with the use of a medicinal product whether or not considered related to this medicinal product.

A serious adverse event (SAE) is any medical occurrence or effect that at any dose:

- Results in death
- Is life threatening
- Requires hospitalization or prolongation of existing inpatient hospitalization
- Results in persistent or a significant disability or incapacity
- Is a congenital anomaly or birth defect
- Is cancer

- Life threatening in the definition of a SAE refers to an event in which the subject was at risk of death at the time of event; it does not refer to an event which hypothetically might have caused death if it were more severe.

12.2 Recording of Adverse Events

At each contact with the subject, the investigator will seek information on AEs by specific questioning and, as appropriate, by examination. Information on all adverse events will be recorded immediately in the source document, and also in the appropriate AE section of the case report form (CRF). All clearly related signs, symptoms, and abnormal diagnostic procedures results will also be recorded in the source document.

The clinical course of each event will be followed until resolution, stabilization, or until it has been determined that the study treatment or participation is not the cause. Serious adverse events that are still ongoing at the end of the study period will be followed up to determine the final outcome. Any SAE that occurs after the study period and is considered to be possibly related to the study treatment or study participation will be recorded and reported immediately.

12.3 Reporting of Serious Adverse Events

12.3.1 Study Sponsor-Investigator Notification by Investigator

A SAE will be reported to the study sponsor-investigator by telephone within 24 hours of the event. A SAE form will be completed by the investigator and faxed to the study sponsor within 24 hours. The investigator will keep a copy of this SAE form on file at the study site. Report a SAE by phone and facsimile to [name], [contact], [contact].

At the time of the initial report the following information will be provided:

- Study identifier
- Study Center
- Subject number
- A description of the event
- Date of onset
- Current status
- Whether study treatment was discontinued
- The reason event is classified as serious
- Investigator assessment of the association between the event and study treatment

Within the following 48 hours, the investigator will provide further information on the AE in the form of a written narrative. This will include a copy of the completed SAE form and any other diagnostic information that will assist the understanding of the event. Significant new information on ongoing SAEs will be provided promptly to the study sponsor-investigator.

12.3.2 IRB Notification by Investigator

Reports of all SAEs (including follow-up information) will be submitted to the Cleveland Clinic Foundation (CCF) IRB per the guidelines of the CCF IRB Standard Operating Procedures. Copies of each report and documentation of IRB notification and response will be filed in the regulatory binder.

The following four types of events will be reported to the IRB (these follow the Case Cancer IRB because this is an anti-cancer agent being used in patients with mild to moderate AD):

1. Adverse events which are serious, unexpected, and related or possibly related to participation in the research.
2. Serious adverse events that are expected in some subjects, but are determined to be occurring at a significantly higher frequency or severity than expected.
3. Other unexpected adverse events, regardless of severity, that may alter IRB analysis of the risk versus potential benefit of the research and, as a result, warrant consideration of substantive changes in the research protocol or informed consent process/document.
4. Unanticipated problems involving risks to subjects or others or any serious or continuing noncompliance with this policy or the requirements or determinations of the IRB.

12.3.3 FDA Notification by Sponsor-Investigator

The FDA will be notified by telephone or by facsimile transmission of any unexpected fatal or life threatening experience associated with the use of the drug as soon as possible, but no later than seven calendar days from original receipt of the information.

If a previous adverse event that was not initially deemed reportable is later found to fit the criteria for reporting, the study sponsor-investigator will submit the adverse event in a written report to the FDA as soon as possible, but no later than 15 calendar days from the time the determination is made.

12.4 Unblinding Procedures

The research coordinator will inform the sponsor-investigator of all subjects whose treatment was unblinded within 24 hours of unblinding. Most unblinding will be part of managing a SAE and will be reported with the SAE. Unblinding that was not associated with a SAE will be reported in a timely manner. This will be done within 24 hours by telephone or facsimile, and will be followed by a written narrative of the reason for unblinding within 24 hours of the event.

12.5 Stopping Rules

If 4 or more patients worsen clinically in a manner greater than expected for untreated AD, the protocol will be stopped. Similarly, if 4 or more patients show ARIA-E or microhemorrhages on the 2nd MRI, the protocol will be stopped.

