4. STUDY DESIGN

This is a 24 week, Phase II, randomized, double blind, placebo controlled, parallel group, proof-of-concept three-site study, to evaluate the effect of rasagiline in the regional brain metabolism on FDG PET in patients with mild to moderate Alzheimer's disease.

The study consists of two phases: a 24-week double blind placebo controlled treatment period with a 4-week follow-up period. Patients will be randomized to a 1:1 ratio at Baseline to receive rasagiline or matching placebo treatment.

The study drug will be given as 0.5 mg dose once daily for the first 4 weeks then increased to 1 mg dose daily tablet for the next 20 weeks. A total of 50 subjects will be enrolled and will be randomized to a 1:1 ratio. Twenty-five participants will receive rasagiline and the other 25 will receive matching placebo for the 24-week treatment period.

Figure 5. **Research Schematic**

Visit 1 – Screening visit (within a 60-day period); MRI, FDG PET and ¹⁸F-AV-1451 Tau imaging

Visit 2 – Baseline (Week 1)

Visit 3 Week 4; increase dose from 0.5 mg QD to 1 mg QD

Visit 4 Week 8

Visit 5 –Week 24; blood draws, FDG PET & ¹⁸F-AV-1451 Tau imaging, end of treatment

Visit 6 – Follow-up Visit/ Week 28; end of study/early discontinuation

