5.4 Subject Withdrawal

Patients and caregivers are informed that they have the right to withdraw from the study at any time without prejudice or loss of benefit to which they are otherwise entitled.

The investigator or sponsor may withdraw a patient from the study in the event of an inter-current illness, adverse event, non-compliance, protocol violation and other reasons concerning the health or wellbeing of the patient.

Following are specific circumstances justifying withdrawal:

- Development of an inter-current medical condition or need for concomitant treatment that precludes further participation in the trial
- Unacceptable toxicity or any adverse event that precludes further participation in the trial
- The investigator removes the patient from the trial in the best interests of the patient
- Non-adherence to study regimen as determined by pill count
- Patient withdraws consent to continued participation in the trial

Patients who withdraw prior to study completion will be asked to return to the clinic to complete visit 6 (end of study) assessments.

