7. DESCRIPTION OF STUDY VISITS

7.1 Visit 1 – Screening (Days -60 to -1)

Subjects will undergo all screening procedures within 60 days prior to baseline visit to confirm the study eligibility.

The following activities will be completed:

- Obtain IRB approved written informed consent from the subject and the subject's legal representative in accordance with regulation before initiating any procedures for both the main protocol and the **¹⁸F-AV-1451 imaging companion** protocol
- Assess inclusion and exclusion criteria
- Obtain demographic data
- Obtain medical history and review medications
- Obtain history of prior procedures (radiation/PET)
- Record prior medication within the last 3 months
- Obtain Ohio State University Traumatic Brain Injury Identification Method (OSU TBI-ID) Questionnaire for the **¹⁸F-AV-1451 TAU imaging companion protocol**.
- Perform Mini Mental State Examination (MMSE)
- Perform physical and neurological examinations
- Record orthostatic vital signs, body weight and height
- Obtain standard single 12 lead EKG
- Collect non-fasting blood sample for routine laboratory test including:
 - Hematology
 - Blood chemistry
 - Liver function
 - TSH
 - B12
- Collect urine sample for screening urinalysis (UA)
- Obtain MRI: T1 sequence and two-dimensional T2*-GRE to detect micro-hemorrhages and T2 FLAIR sequences to identify ARIA-E
- Obtain fluorodeoxyglucose (FDG) PET imaging
- Obtain **¹⁸F-AV-1451** Tau imaging pending positive FDG PET imaging results

The screening visit MRI, FDG PET imaging and **¹⁸F-AV-1451** Tau PET imaging visits will be done on separate visits.

POST ¹⁸F-AV-1451 TAU IMAGING FOLLOW-UP PHONE CALL

A follow-up phone call to the participant or the caregiver will be conducted between 2 and 3 business days after the imaging visit, but not before 48 hours post-injection, to confirm participant well-being and to collect information about any new adverse events. If both of these days are not business days, the follow-up phone call can occur the following business day.

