7.2 Visit 2 – Baseline (Day 1)

Patients will be randomized within 60 days from the first day of screening.

The following activities will be completed PRIOR to dosing:

- Review Inclusion/Exclusion qualification
- Review laboratory studies performed at Screening Visit (laboratory results should be normal to continue randomization of subject)
- Review of MRI and PET Scan results
- Inquire about occurrence of adverse events since previous visit and changes to concomitant medications

If subject continues to be eligible for the study, he/she may be entered into the double-blind randomization phase and procedures listed below will occur:

- Record vital signs and body weight
- Perform Mini Mental State Examination (MMSE)
- Collect blood sample for ApoE genotyping test
- Collect blood sample for biomarker measures including:
 - Serum A β 40 and 42
 - sAPP- α , sAPP- β , Isoprostanes
 - Cytokines and other measures relevant to AD
- Perform the following assessments:
 - ADAS-Cog 11
 - CGIC
 - NPI
 - ADCS-ADL
 - Digit Span
 - COWAT
 - QoL-AD/Study Partner
- Dispense double blind study medication to patient and caregiver for outpatient dosing, with instructions to return bottle and unused study medication to clinic at next visit.
- Provide instructions to caregiver/subject on outpatient dosing, including storage, administration, and compliance assessment.

Patients will be given a one-month supply of medication at this visit. The dosing instruction at this visit is to take one 0.5mg capsule of study drug or matching placebo once a day for one month. Leftover medications will be brought to clinic visits for accountability.

7.3 Visit 3 – Week 4

This visit will occur at the end of Week 4 with a visit window of +/- 5 days.

The following activities will be completed:

- Record orthostatic vital signs and body weight
- Inquire about occurrence of adverse events since previous visit and any changes to concomitant medications since Baseline Visit
- Perform the following assessments:
 - ADAS-Cog 11
 - CGIC
 - NPI
 - ADCS-ADL
 - Digit Span
 - COWAT

- Assess drug adherence and accountability of study medication
- Dispense double blind study medication to patient and caregiver for outpatient dosing, with instructions to return bottle to clinic at next visit.
- Provide instructions to caregiver/subject on outpatient dosing, including storage, administration, and compliance assessment.

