7.7 Unscheduled Visits

Patients will have unscheduled visits if they report unusual side effects. If the patient reports abrupt worsening of cognition, or experiencing one of the reported adverse effects, the patient will be evaluated by the study clinician.

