9.9 MRI

A research grade (ADNI quality) MRI, acquired for each subject at the time of enrollment, will also be provided. T1, T2 and FLAIR or T2* sequence will be collected.

3D Sagittal T1 sequence: T1-weighted MPRAGE or MPRAGE-like sequence adhering to the Alzheimer’s disease Neuroimaging Initiative (ADNI) specifications. Typical scanner sequence parameters that could be used include:

Scanner	Sequence	Type	TR (ms)	TE (ms)	TI (ms)	NEX/NSA	Flip Angle(°)	Bandwidth
Siemens 3T	3D MPRAGE	(tfl)	2300	2.98	TI = 900	1	9	240 Hz/px
GE 3T	3D	IR-FSPGR	--	Min full	TI = 400	1	11	31.25 kHz
Philips 3T	3D	T1-TFE	Shortest	Shortest	TFE delay=900	1	9	Water-fat shift=1.8

All scans in this study will be evaluated using a stringent quality control procedure to ensure suitability for analysis. Quality control will be performed within 3 business days of image receipt so that in the event of an issue, the visit may be rescheduled if issues cannot be addressed through re-reconstruction. Quality control steps will include header checks, visual inspection, and quantitative inter-frame motion measurement. Image headers will be checked to ensure that the protocol was followed with regard to injected dose, injected volume, and start time after injection, number of frames, scan duration, and reconstruction parameters. Visual inspection will include checks for anatomical truncation (e.g., omission of lower slices of cerebellum), adequate image counts, and image noise such as streaking, image blur indicative of subject motion, asymmetry indicative of misalignment between emission and transmission scan, and other apparent artifacts. Quantitative motion measurement will involve calculation of the inter-timeframe translation and rotation, with preset thresholds above which a frame (or scan, if multiple frames) will not be accepted as suitable for analysis.

ADMdx has developed and will utilize an automated image processing pipeline, PETMAX™, which has secure user access, version control with back-up, and complete audit trail for use in clinical trials. PETMAX facilitates user interaction for visual inspection and quality control at multiple stages in the pipeline, and streamlines the execution of the many steps (including SPM functions) employed in image preparation and analysis. Results are logged and saved under version control.

9.10 [18F]-FDG-PET Imaging

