There are two FDG-PET scans to be conducted per participant in this study. The scans will be done at the Screening visit for study eligibility, and at Week 24 visit for end of treatment scan and comparison.

The scanning protocol and equipment qualification requirements for this study will be consistent with those implemented in ADNI 2 (30). FDG-PET imaging data will be obtained at two sites: the Cleveland Clinic facilities in Cleveland, Ohio and Las Vegas, Nevada. Each of these sites uses a Siemens Biograph PET/CT LSO 16 slice camera. As part of site qualification, site practices will be reviewed, along with recent equipment calibration logs. If the site has a 3D-Hoffman phantom

scan collected within the past 12 months available, the scan will be provided for examination. If a de-identified patient brain scan can be made available, it will be provided for examination. The requirements for subject management in preparation for the scan, during FDG uptake, and during image acquisition will be reviewed with staff to ensure that these can be met. Since the Cleveland Clinic participates in ADNI as well as numerous other clinical trials, it is anticipated that requirements will be met.

The scanner will have an up-to-date calibration and normalization on the date of each imaging session. A daily QC check will be done at the beginning of the day the scanning will be completed. The scan will be visually inspected for abnormalities. If there is a possibility that the abnormality could impact the PET scan quality, the visit will be rescheduled.

Daily CT quality assurance will be performed as recommended by the specific vendor, and should typically include a "checkup/calibration" procedure and a water phantom scan. The checkup/calibration procedure guarantees optimum image quality by warming up the x-ray tube and should be performed at startup and within 1 hour prior to any scan. The water phantom provides quality measurements of 3 parameters. The parameters are the CRT value of water calculated in Hounsfield units (HU), the pixel noise of images calculated as a standard deviation, and the tube voltages measured directly on the x-ray tubes. These three measurements should be determined for all available kVp values.

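### The MRI stopping rule in protocol 12.5 depends on a second MRI that the supplied documents never schedule

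*Protocol*

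**What the plan says.** Protocol section 12.5 has two stopping criteria. The first concerns clinical worsening. The second reads: "if 4 or more patients show ARIA-E or microhemorrhages on the 2nd MRI, the protocol will be stopped".

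The MRI itself appears in these places:

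- Section 7.1 (Screening) orders a T1 sequence and "two-dimensional T2*-GRE to detect micro-hemorrhages and T2 FLAIR sequences to identify ARIA-E".
- The schematic in section 4 puts it at Visit 1: "Screening visit (within a 60-day period); MRI, FDG PET and" tau imaging.
- Section 7.2 (Baseline) lists, among the steps before dosing, "Review of MRI and PET Scan results".
- Section 9.9, repeated in Appendix A, says: "A research grade (ADNI quality) MRI, acquired for each subject at the time of enrollment, will also be provided".
- Table 2 and Appendix B each have an MRI row with a single mark, under Screening.

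Brain MRI findings are named as a safety measure in the Synopsis secondary objectives and in SAP section 3.2. They are absent from the safety objective in protocol 3.2, the endpoint lists in the Synopsis and protocol 3.4, and the Synopsis safety row.

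**The concern.** A stopping rule needs an assessment that can trigger it. This one reads a second MRI, with the definite article, as though the scan were a planned part of the study. If no such scan is planned, the count of patients with findings stays at zero whatever happens on treatment, and the protocol promises a safeguard that its own schedule does not supply. The sequences meant to detect microhemorrhage and ARIA-E are ordered only before exposure, so the scheduled MRI cannot show a change on drug.

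This matters more because section 12.6.1 and the Synopsis state that no data safety monitoring board is needed. The written rules in 12.5 are then the only explicit triggers for stopping the trial.

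**Working it through.** The plan states no power or sample-size figure on this point, so there is nothing to reproduce. The check is a count of scheduled MRIs.

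**Step 1: every place that schedules procedures**

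| Place in the protocol | MRI listed? |
|---|---|
| 7.1 Screening, Days -60 to -1 | Yes |
| 7.2 Baseline | Review of the earlier result only |
| 7.3 Week 4 | No |
| 7.4 Week 8 | No |
| 7.5 Week 24 | No |
| 7.6 Week 28 / early discontinuation | No |
| Section 4 schematic | Visit 1 only; the Week 24 line has blood draws, FDG PET and tau imaging |
| Table 2 and Appendix B | One mark, at Screening |
| 9.9 and Appendix A | At enrollment |

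**Step 2: is a repeated procedure normally shown as repeated?** Yes. In Table 2 and Appendix B, FDG PET, tau PET, ECG and laboratory tests each carry two marks, at Screening and Week 24. Section 9.10 also gives the number of FDG scans outright: "There are two FDG-PET scans to be conducted per participant in this study". The image-processing text in Appendix A uses one MRI per subject, co-registered to the baseline PET, and describes only the PET scans as longitudinal.

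**Step 3: other routes to a second MRI**

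- Patients who withdraw early "will be asked to return to the clinic to complete visit 6 (end of study) assessments". Visit 6 has no MRI.
- At unscheduled visits (7.7), "the patient will be evaluated by the study clinician". Imaging is not mentioned.
- Quality control in 9.9 allows a visit to be rescheduled after a technical failure. That would replace the enrollment scan; it is not described as an on-treatment safety scan.
- The tau companion protocol (9.11) was not supplied. Table 2 already carries tau-related items, namely tau PET, the follow-up call and the OSU TBI-ID, and shows no further MRI with them.

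**Step 4: the count**

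- Scheduled MRIs per patient: 1 + 0 + 0 + 0 + 0 + 0 = 1 over six visits.
- Scheduled MRIs after the first dose: 0 over four visits (Weeks 4, 8, 24 and 28).
- With 50 patients: 50 × 1 = 50 MRIs before dosing and 50 × 0 = 0 after.
- Patients needed for the rule: 4, or 4/50 = 8% of those enrolled. With no second MRIs, P(4 or more) = 0 at any true event rate.

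**Step 5: illustration only.** Assume that all 50 patients had a second MRI and that each had probability p of a finding. The documents give no value for p, so a range is shown. Then P(4 or more of 50) = 1 − Σ(k = 0 to 3) C(50, k) p^k (1 − p)^(50−k):

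| p | P(4 or more of 50) |
|---|---|
| 2% | 0.018 |
| 5% | 0.24 |
| 10% | 0.75 |
| 15% | 0.954 |
| 20% | 0.994 |

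The criterion would be a working rule if the scan it refers to existed. Under the schedule as written, every entry in the right-hand column is 0.

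**The case against.** The strongest reply is that this may be a leftover sentence of little practical weight. The risk sections for rasagiline (1.3 and 10.1) mention neither ARIA-E nor microhemorrhage. The primary FDG PET endpoint and its analysis are untouched. Adverse event review, vital signs, unscheduled visits and the medical monitor all work without this criterion. For-cause imaging is not ruled out and the companion protocol was not seen, so it would go too far to say that no second MRI could ever be done.

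Much of this stands as a limit on scope. The supported statement is that no second MRI is scheduled in the supplied documents. It does not remove the contradiction: 12.5 is current text, it commits the sponsor to stop the protocol, and it conflicts with every scheduling section. Even if the companion protocol contained an MRI, the main protocol's rule and schedule would still need to agree.

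On the safety objective, silence about MRI in protocol 9.1 and SAP section 11 proves little. Section 9.1 also leaves out ECG, and SAP section 11 leaves out both ECG and laboratory data. The SAP is a draft dated September 2014, and its section 3.2 still names CIBIC+ and ADAS-Cog13, both replaced by Amendment 1, so its MRI wording may be equally old. The disagreement therefore rests on the Synopsis objectives and SAP 3.2 against protocol 3.2, the two endpoint lists and the Synopsis safety row. It is real, but secondary.

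**Conclusion.** The concern holds. Section 12.5 contradicts the imaging schedule: one MRI per patient, before dosing, and none at the four post-baseline visits. No scheduled assessment in these documents can trigger the MRI criterion, so one of the two stopping rules cannot operate as written. This must be corrected because it is a stated rule for stopping the trial and there is no monitoring board behind it.

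The conclusion rests on the supplied protocol and SAP alone. It assumes that the companion tau protocol adds no MRI and takes no account of imaging done for cause. It does not extend to the rest of the safety monitoring, and it does not affect the efficacy analysis.

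**What to change.** Reconcile section 12.5 with sections 4, 7.1 to 7.6 and 9.9, Table 2, and Appendices A and B, so that the stopping criterion and the scheduled imaging agree. Check the companion tau protocol at the same time. State the safety objective identically in the Synopsis, protocol 3.2 and SAP 3.2, and make the endpoint lists, the Synopsis safety row, protocol 9.1 and SAP section 11 consistent with it.

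The sponsor must decide which passages give way; no schedule, threshold or clinical rule is proposed here. The minimum cost is amendment wording in the protocol and Synopsis and one line in a SAP that is still a draft. Any further cost depends on whether the sponsor's resolution involves imaging.
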